9.3 Definition of Populations

We will use different ways to summarize and analyze our data based on the type of outcome and variable that we are interested in.

9.3.1 Intention-to-treat (ITT) analysis

For outcomes that are continuous variables, which are numerical and can take any value within a range, we will use the ITT approach, which is a way of comparing the groups based on their original random assignment to a treatment, regardless of what treatment they actually received or completed. This helps to avoid bias from factors that may influence the results, such as dropout, which is when subjects leave the study before it ends, or crossover, which is when subjects switch to a different treatment than they were assigned to. The ITT approach is also simpler than other ways of analyzing the data that need to consider whether the subjects followed the treatment as planned or not.

9.3.2 Per protocol (PP) analysis set

For outcomes that are categorical variables, which are non-numerical and can belong to one of several groups or categories, we will use the PP analysis set, which is a subset of subjects who followed the protocol without major deviations that could affect the outcomes. The protocol is the plan or procedure that we use to conduct the study. Deviations are when subjects do not follow the protocol as expected. For example, this includes patients who used other medications that were not allowed by the protocol or who did not follow the protocol properly. We will decide who to include or exclude in the PP analysis set before we lock the database, which is when we finalize the data after checking and cleaning them.

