5.2 Adherence Assessment

Upon enrollment, all participants will be required to complete all relevant intervention treatments, as well as subsequent questionnaire surveys and efficacy assessments, without any interruption to the intervention treatment.

6. STUDY PROCEDURES.

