For data that are not normally distributed or have heterogeneous variance, we will use the Kruskal-Wallis test to compare the groups. The Kruskal-Wallis test is suitable for comparing three or more groups with continuous data that do not meet the assumptions of ANOVA. We will report the data and their change using median and IQRs, which show the middle and range of the data. Additionally, we will perform posthoc comparisons between groups using the Wilcoxon rank-sum test, which can compare two groups with continuous data that do not meet ANOVA assumptions. We will report these comparisons using the HL estimate of location shift and 95% confidence intervals, which show how much one group differs from another group in terms of location or central tendency. We will also report an adjusted P value for each comparison.

We will assess and compare how participants perceive their improvement from enrollment in the study to 4 and 8 weeks after treatment initiation. This subjective outcome reflects how participants feel about their condition and treatment, which we will measure using a rating scale with categories such as much better, better, about the same, or worse. Since this is non-numerical, ordered categorical data, we will use the PP analysis set to analyze the subset of subjects who adhered to the protocol without major deviations. We will apply the Kruskal-Wallis test to compare groups based on their ratings of improvement at different time points, reporting the data using frequency and percentile. We will use a two-tailed P-value to determine statistical significance, setting a cutoff of less than .05, unless specified otherwise.

Additionally, we will record and compare participant satisfaction with the current treatment and their willingness to receive another therapy. This dichotomous outcome measures whether participants answered yes or no to whether they would like to receive another therapy. We will use the PP analysis set and the chi-square test to compare the groups based on their responses at different time points. We will report the data using frequency and percentile, and consider a P-value of less than .05 to be statistically significant, unless specified otherwise.

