10.3.2 Protocol Deviations

Any protocol deviations will be recorded in the protocol deviation log and reviewed with the study PI at weekly meetings.

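### The per-protocol set is the only analysis set for two self-reported secondary outcomes, but the plan does not say who decides membership, whether they are masked, or what measurable rule they apply

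*Combined protocol and SAP*

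**What the plan says.** Section 9.3.2 assigns categorical outcomes to the per-protocol set, described as "a subset of subjects who followed the protocol without major deviations that could affect the outcomes". It does not define a major deviation. Its examples of deviators are "patients who used other medications that were not allowed by the protocol or who did not follow the protocol properly". On procedure it says only: "We will decide who to include or exclude in the PP analysis set before we lock the database".

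Section 9.5.2 applies this set to two outcomes. For perceived improvement, an ordered rating compared by Kruskal-Wallis, "we will use the PP analysis set to analyze the subset of subjects who adhered to the protocol without major deviations". For satisfaction with the current treatment and willingness to receive another therapy, a yes/no answer, "We will use the PP analysis set and the chi-square test to compare the groups based on their responses at different time points". No intention-to-treat or all-randomized analysis is given for either.

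Section 5.2, headed Adherence Assessment, states a requirement: treatment and assessments are to be completed "without any interruption to the intervention treatment". It names no measure and no threshold. Section 10.3.2 adds: "Any protocol deviations will be recorded in the protocol deviation log and reviewed with the study PI at weekly meetings".

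**The concern.** A per-protocol list agreed before lock is safe from selective exclusion only if the people agreeing it cannot see arm and outcome, or if the criteria leave them nothing to judge. The plan states neither. By the time of lock the Week 4 and Week 8 ratings exist, and the ground "who did not follow the protocol properly" leaves membership to judgement.

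Both outcomes are self-reported by children and parents who know the treatment. If children with poor ratings are more likely to be classed as deviators in one arm than in another, the comparison shifts, and no full-set result is planned that would show it.

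The grounds for exclusion are also unequal by arm. Missed doses can be a deviation only in the two drug arms, because urotherapy alone has no doses to miss. Section 7.1 removes a child with solifenacin side effects from the study but classes vitamin D reactions as unsafe, while section 8 stops the intervention for any drug-related adverse effect or worsening of symptoms. The plan does not say whether such children count as deviators. If they do, membership depends on arm and on response.

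**Working it through.** **1. What is specified and what is not**

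| Element | Where | What is stated |
|---|---|---|
| When the list is fixed | 9.3.2 | Before database lock |
| Who fixes it | 9.3.2 | Not stated (only 'we') |
| Masking of that step | 9.3.2 | Not stated |
| Roles masked elsewhere | 6.2.3, 10.1, 10.3.1 | Outcome assessors, statisticians, clinicians and evaluators giving the scales, urotherapy trainers |
| Study PI | 10.3.2 | Reviews deviations weekly; not listed as masked |
| Visit adherence | 10.2 | Collected |
| Compliance with treatment | 10.1 | Reviewed regularly; no method of measurement |
| Current medications | 6.1 | Run-in, Week 4, Week 8 |
| Serum vitamin D | 6.2.4, 7.2 | Measured at follow-up |
| Dose count or other intake record, with cut-off | none found | Not given |

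The disallowed-medication ground can be checked against recorded data. The other ground cannot, as far as drug intake is concerned.

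**2. Arm size for the illustration**

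Section 9.2 gives 87 per group and 10% attrition: 87/(1 − 0.10) = 96.7, rounded up to 97, as the plan states. No sample size is given for the per-protocol set or for these two outcomes.

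**3. Assumed one-arm worst case, yes/no outcome only**

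The counts are assumptions. A favourable answer means not wanting another therapy. The test is the planned chi-square, the sum of (observed − expected)²/expected over three arms, 2 df.

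| Scenario | Arm A | Arms B and C, each | Chi-square | P |
|---|---|---|---|---|
| All randomized | 58/97 (59.8%) | 48/97 (49.5%) | 2.76 | 0.252 |
| 5 unfavourable removed from A | 58/92 (63.0%) | 48/97 | 4.62 | 0.099 |
| 10 unfavourable removed from A | 58/87 (66.7%) | 48/97 | 7.16 | 0.028 |
| 10 unfavourable removed from every arm | 58/87 | 48/87 (55.2%) | 3.17 | 0.205 |
| 10 removed per arm, roughly in proportion | 52/87 | 43/87 | 2.49 | 0.288 |

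In the third row, 10 of arm A's 39 unfavourable responders (26%) are removed, with no favourable responder and nobody from the other arms. The last two rows show that a similar number of exclusions does little when they are spread evenly.

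**4. Type I error under the same mechanism**

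Simulation with assumed rates: three arms of 97, equal true favourable rate p, chi-square at 0.05, 20,000 replicates. In one arm a share e of unfavourable responders is excluded, so that arm's expected rate becomes p/[p + (1 − p)(1 − e)]. For p = 0.5 and e = 0.2 this is 0.5/0.9 = 55.6%.

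| Exclusion in one arm | p = 0.5 | p = 0.7 |
|---|---|---|
| None | 5.2% | 5.0% |
| 10%, unrelated to answer | 5.2% | 4.8% |
| 20% of unfavourable | 11.4% | 9.7% |
| 30% of unfavourable | 20.7% | 17.1% |
| 40% of unfavourable | 37.0% | 29.5% |

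Selective exclusion inflates the error; exclusion unrelated to the answer does not. Neither calculation is applied to perceived improvement, for which the plan specifies Kruskal-Wallis on the ordered categories.

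**The case against.** A reader might infer that people who know each child's arm and rating will draw up the list, that the trial is open, and that adherence is not measured at all. The documents support none of these.

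- **Masking.** Section 9.3.2 is silent; it does not say the step is unmasked. Statisticians and assessors are masked, the analyst sees coded data (6.2.3), and the biostatisticians manage the database (10.2). Nothing says the PI sets the list, only that deviations are reviewed with the PI.
- **Design.** The trial is observer-blind with unmasked participants (sections 3, 6.2.3 and 9.2).
- **Adherence.** Visit adherence, current medications and serum vitamin D are recorded. What is missing is a drug-intake measure and a cut-off.
- **Timing.** Fixing a per-protocol set before lock is usual practice, deviations are logged as the trial runs, and analysis waits until completion. The timing is not the fault.
- **Size.** The P = 0.03 example is a worst case in one arm, and the 10% attrition in section 9.2 is no evidence that 10 children would be excluded selectively.
- **Reach.** Only two secondary outcomes are involved.

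All of this stands, and it narrows the point. It does not supply the missing decision-maker, masking statement or criterion, nor a second analysis set for the two outcomes.

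**Conclusion.** The point holds in limited form and should be corrected. Per-protocol membership for two self-reported secondary outcomes rests on an open-ended criterion, applied by unnamed people whose masking is not stated, with no drug-intake measure or cut-off. The primary and continuous secondary outcomes use intention-to-treat (9.3.1, 9.5.1), and the safety analysis uses the per-protocol set only as sensitivity (9.3.3), so the main conclusions of the trial are not at risk from this.

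The size cannot be derived from the documents, because they give no expected response or exclusion rates. With assumed rates, selective exclusion in one arm raises the type I error of the yes/no comparison from 5% to between about 10% and 37%; exclusion unrelated to the answer leaves it at about 5%. The documents give no evidence that selective exclusion is intended or likely. The finding is that the plan does not rule it out.

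**What to change.** 1. In 9.5.2, analyse both outcomes in all randomized children as the main analysis, with per-protocol as sensitivity, and align 9.3.1 and 9.3.2. This matters most: masking does not remove the bias of excluding children after randomization, and a drug count can exclude children only from the drug arms. Section 9.5 plans multiple imputation for continuous data only, so a rule for missing ratings must be added.
2. In 9.3.2, state that the list is fixed before lock and before treatment codes are released, by reviewers who see the deviation log with arm and all outcome fields removed.
3. Replace the open-ended ground with criteria set before the first child is randomized and based on recorded data: urotherapy session attendance in all three arms, disallowed medication, and returned study drug counted at Weeks 4 and 8 in the drug arms.
4. Report exclusions by arm and reason.
5. Reconcile sections 7.1 and 8 on removal from the study and stopping of treatment, and say how children affected by them are handled in each analysis set.

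The cost is plan wording, a masked export of the log with light recoding of entries that name a drug, and a return count at two existing visits.

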9.3.3 Safety analysis set

For safety analysis, which is when we assess the safety and side effects of the treatment, we will use the SS set, which is a subset of all patients who took at least one dose of the study drug and have safety records in the database. The database is where we store and manage our data electronically. We will only use measured values for this analysis, which are values that we actually observed and recorded for each subject. We will also do a sensitivity analysis using the PP analysis set, which is when we test how

robust our results are to different assumptions or scenarios.

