1. STUDY OBJECTIVES

The purpose of this study was to assess the clinical efficacy and safety of highdose Vitamin D Supplementation (VDS) in combination with Standard Urotherapy (SU) for the treatment of Overactive Bladder (OAB) dry among pediatric patients, as compared to (1) solifenacin, a commonly utilized anticholinergic medication, combined with SU, and (2) SU alone. This study endeavors to contribute to the current understanding of the optimal treatment approach for managing OAB dry in this population and has the potential to inform clinical decision-making and improve patient outcomes.

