5. STUDY INTERVENTIONS

5.1 Interventions, Administration, and Duration

During the eight-week treatment period, the study was divided into three intervention groups, and each patient received follow-up care from an outpatient physician every four weeks. Participants in each intervention group will be required to attend a 30-minute SU program per session.

Children assigned to the VDS+SU group will receive high-dose VDS (800 IU, three times per day) in addition to the biweekly SU course.

Children in the SOL+SU group will receive treatment with solifenacin succinate (5 mg once daily, with a maximum dose of 10 mg per day), in addition to the SU course.

Participants in the SU group only attend regular SU meetings, which provide basic information and an explanation of the disease, guidance on behavioral changes and lifestyle advice, registration of urinary habits using a bladder diary, as well as support and encouragement from caregivers.

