7.1 Specification of Safety Parameters

Participants were required to take solifenacin and high-dose VDS as part of the study. Anticholinergic side effects, including dry mouth, blurred vision, constipation, and nausea, among others, may occur due to solifenacin use. If any of these symptoms occur, the medication will be discontinued, and the participant will be removed from the study. Over-supplementation of vitamin D can lead to symptoms of vitamin D toxicity, including anorexia, nausea, diarrhea, constipation, irritability, and somnolence. Any occurrence of these adverse drug reactions or serum vitamin D levels exceeding 100 ng/mL will be evaluated as unsafe.

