7.3 Adverse Events and Serious Adverse Events

The study may result in adverse events related to medication side effects of solifenacin and high-dose VDS. Adverse events and serious adverse events will be classified based on the severity and intensity of the side effects.

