9. STATISTICAL CONSIDERATIONS

9.1 General Design Issues

Objective: The aim of this randomized controlled trial is to examine the effectiveness and safety of high-dose VDS plus SU for managing OAB-dry symptoms in pediatric patients with low vitamin D levels (<35ng/mL).

Specific Aim 1: The main outcome is the difference in post-treatment improvement between children who receive high-dose VDS plus SU and those who receive solifenacin plus SU or SU monotherapy for OAB-dry symptoms. The study expects that high-dose VDS plus SU will lead to more improvement than SU monotherapy and solifenacin plus SU. Furthermore, SU monotherapy will result in less improvement than solifenacin plus SU.

Specific Aim 2: The secondary outcome is the safety profile of high-dose VDS plus SU for OAB-dry symptoms in pediatric patients. The study anticipates that the safety profile of high-dose VDS plus SU will be similar to that of solifenacin plus SU or SU monotherapy at follow-up.

The study design is an 8-week randomized controlled trial, and all treatments will be administered in a group setting. Pediatric patients with OAB-dry symptoms will undergo 8 weekly sessions of high-dose VDS plus SU, solifenacin plus SU, or SU monotherapy. Independent assessors will evaluate the patients before the treatment, at mid-treatment (4-week follow-up), and at the 8-week follow-up to test the expectations. To account for attention, time, and group effects, all SU sessions will be administered in a group setting.

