9.5.3 Safety analysis

The safety analysis will be performed using the Safety Analysis Set, which will assess treatment-emergent adverse events (TEAEs). Detailed recordings of all severe adverse events and TEAEs leading to discontinuation from the study will be included. Changes in clinical laboratory parameters and vital signs at each scheduled time point from baseline will be summarized according to treatment groups.

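### The safety set requires a dose of study drug, so no child treated as assigned to standard urotherapy (SU) alone can enter it, although the plan compares safety with SU alone

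*Combined protocol and SAP*

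**What the plan says.** All references are to the combined protocol and SAP.

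- **Who enters the safety set.** Section 9.3.3 defines it as "a subset of all patients who took at least one dose of the study drug and have safety records in the database". Both conditions must be met. The same section adds a sensitivity analysis in the per-protocol set.
- **What the arms receive.** Section 5.1 gives one arm high-dose vitamin D plus SU and another solifenacin plus SU. For the third arm, "Participants in the SU group only attend regular SU meetings".
- **What counts as drug.** Section 7.1 names solifenacin and vitamin D. Section 7.3 expects "adverse events related to medication side effects of solifenacin and high-dose VDS". Neither section, nor any other, calls urotherapy a study drug.
- **What is to be compared.** Section 1 sets the efficacy and safety of vitamin D plus SU "as compared to (1) solifenacin, a commonly utilized anticholinergic medication, combined with SU, and (2) SU alone". Specific Aim 2 in 9.1 anticipates that "the safety profile of high-dose VDS plus SU will be similar to that of solifenacin plus SU or SU monotherapy at follow-up".
- **How safety is analysed.** Section 9.5.3 assigns the safety analysis, including treatment-emergent adverse events, to the safety set. It adds: "Changes in clinical laboratory parameters and vital signs at each scheduled time point from baseline will be summarized according to treatment groups".

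**The concern.** The plan asks a safety question about three arms and names a set that can hold only two of them. An SU child could qualify only by taking a study drug against allocation, and would then no longer represent SU alone.

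The SU arm is the only one that shows how often symptoms arise without a drug. Section 7.1 lists nausea and constipation both as solifenacin side effects and as signs of excess vitamin D. If only the two drug arms are tabulated, similar rates of these symptoms could mean that both drugs are well tolerated or that both cause them, and the table could not tell the two apart.

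If the analysts add the SU children because three arms were evidently meant, they apply an inclusion rule that the plan does not contain. They must also choose when the event window opens in an arm that has no first dose.

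**Working it through.** This is a check of set membership. It uses only arm sizes and needs no event rate.

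**Inputs**

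- 87 evaluable per group, 10% attrition, 97 recruited per group, about 300 in total (9.2).
- Three arms; drug is assigned in two of them (5.1).
- Membership rule: at least one dose and a safety record (9.3.3).

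**Step 1: the plan's own recruitment figure.** 87 / (1 − 0.10) = 96.7, rounded up to 97 per group. This matches 9.2. The total is 3 × 97 = 291, which the plan rounds to about 300.

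**Step 2: apply 9.3.3 to children treated as assigned.**

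| Arm | Planned | Can meet the dose condition |
|---|---|---|
| Vitamin D + SU | 97 | up to 97 |
| Solifenacin + SU | 97 | up to 97 |
| SU alone | 97 | 0 |
| Total | 291 | up to 194 |

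194 / 291 = 66.7%. The excluded 97 / 291 = 33.3% are the whole SU arm. With the rounded total the share is the same: 200 / 300 = 66.7%.

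**Step 3: set this against the stated comparisons.** In the designated set, vitamin D plus SU against solifenacin plus SU has at most 97 against 97. Vitamin D plus SU against SU alone has at most 97 against 0.

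**Step 4: look for another route into the analysis.**

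- *Intention-to-treat (9.3.1).* This covers continuous outcomes in general and would include SU children's laboratory values. Sections 9.3.3 and 9.5.3 are specific to safety and name a different set. Adverse events are not continuous, so 9.3.1 does not reach them.
- *Per-protocol (9.3.2, 9.3.3).* This can include SU children, but only as a sensitivity analysis and only those who adhered to the protocol. Section 7.1 also provides that children with anticholinergic side effects leave the study. The plan does not say whether they would count as per-protocol; if not, this set would lose events that matter.

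Neither route supplies the three-arm safety analysis of Aim 2.

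**Step 5: are the data collected?** Section 6.1 schedules adverse events at weeks 4 and 8 and laboratory tests at enrolment and week 8, with no exception by arm. Section 7.2 gives all enrolled participants visits every four weeks.

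**Step 6: after correction.** Admitting the SU arm gives up to 194 + 97 = 291 of 291, and 97 against 97 for vitamin D plus SU against SU alone.

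**The case against.** The strongest reply is that this is a slip of wording and the intent is plain. Section 9.1 treats all three regimens as treatments, Aim 2 names SU monotherapy, and 9.5.3 summarises by treatment group. The document is loose elsewhere: "Participants were required to take solifenacin and high-dose VDS as part of the study" in 7.1, read literally, gives both drugs to every child. The counts above merely restate the definition by arm; they measure neither bias nor loss of precision. Safety is the secondary aim, 9.5.3 has no between-group test or margin, and the primary result and sample size are untouched.

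Much of this stands. Three arms were very probably intended, and the practical consequence is small. But evident intent shows that the stated rule is wrong; it does not supply the right one. A descriptive table still needs its comparator column.

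A second objection is that correcting 9.3.3 alone may not be enough. Section 7.2 describes the visit questionnaire and examination as looking for drug-related effects, so events in SU children might be under-recorded. That is fair, and the fix therefore covers elicitation. It is also true that 6.1 has no row for vital signs. However, 9.5.3 already plans vital-sign summaries for the treatment groups, so that gap affects all arms and does not arise from this change.

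A third objection is that the proposed rule uses exposure in the drug arms and randomisation in SU. One could instead admit children who began their assigned intervention. That is workable in principle, but for SU it needs a dependable first session after randomisation, and the plan does not give one. The schedule in 6.1 marks SU on Day 1, before the run-in and randomisation, and then not until Week 4 (Day 33-39). Sections 5.1, 6.1 and 9.1 also disagree on session frequency. The difference in practice is modest: the first scheduled adverse-event record is also at Week 4, so it concerns mainly children with events reported spontaneously before then (section 7 encourages such reports).

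**Conclusion.** The concern holds. Section 9.3.3 conflicts with section 1, Specific Aim 2 and 9.5.3. In the designated set 0 of 97 SU children qualify, the set holds at most 194 of 291 (66.7%), and one of the two stated safety comparisons has no comparator.

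This rests on children being treated as assigned and on study drug meaning vitamin D or solifenacin, the only medicines that the plan assigns. If it meant vitamin D alone, the solifenacin arm would drop out too.

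The point should be fixed but does not threaten the trial. No efficacy analysis depends on it, and nothing is lost if the text is corrected before database lock.

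**What to change.** Before database lock:

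1. **Redefine the set in 9.3.3.** Include children in the two drug arms who took at least one dose of study drug, plus all children randomised to SU, in each case with at least one post-randomisation safety record. Do not make attendance at an SU session a condition.
2. **Account for the undosed.** List drug-arm children who never took study drug separately, under their randomised arm.
3. **Open the event window.** State that events in the SU arm count from randomisation, because 9.5.3 counts treatment-emergent events and this arm has no first dose.
4. **Report all three arms.** Give adverse events, laboratory changes and vital-sign changes for each arm. State in 7.2 that adverse events are elicited in the same way in every arm, whether or not a drug was assigned.

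The cost is a few sentences in 9.3.3, a short clarification in 7.2 and one SU column in each safety table. Adverse-event and laboratory assessments need no additions to the schedule, since 6.1 and 7.2 already apply to every arm.
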